11.1.2.2. Other Secondary Assessments

- OCA (OCA, tauro-OCA, glyco-OCA, total OCA, OCA-glucuronide) and C4 will be assayed to determine bioanalytical concentrations. Additional analyses may include other conjugates or metabolites not yet identified.
- Quality of Life questionnaires. The following patient-reported outcomes will be used to evaluate the effects of OCA compared to placebo on improvements in health-related quality of life:
 - PBC-40: The PBC-40 is a validated disease-specific 40-question quality of life questionnaire, which consists of 6 domains: General Symptoms, Itch, Fatigue, Cognitive Function, Social, and Emotional ([Jacoby 2005](#)).
 - EQ-5D-5L: The EQ-5D-5L consists of 2 sections – the descriptive system and the visual analogue scales (VAS). The descriptive system is organized into 5 dimensions: mobility, self-care, usual activities, pain/discomfort, and anxiety/depression. Each dimension has 5 levels: no problems, slight problems, moderate problems, severe problems, and extreme problems. The VAS records the respondent's self-rate health on a 20 cm vertical line with endpoints labelled "the best health you can imagine: and "the worst health you can imagine" ([Herdman 2011](#), [Oemar 2013](#)).
 - Fatigue Impact Scale (FIS): The FIS is a validated 40 question questionnaire organized into 3 dimensions: cognitive, physical, and social. Each dimension has

5 levels: no problem, small problem, moderate problem, big problem, and extreme problem (Fisk 1994).

11.1.2.3. Other Exploratory Evaluations

- A genetics study for single-nucleotide polymorphisms (SNPs) that may be involved in PBC will be conducted for subjects and at study sites willing to provide samples at Day 0, Month 12, and every other year at the yearly visits thereafter. RNA expression resulting from treatment with OCA will be assessed at indicated timepoints during the study. Subjects will be permitted to decline to provide a blood sample for the genetics study, without affecting their involvement in the study. IRB/IEC review and approval will be required and willing subjects must specifically consent to participate in this evaluation. The samples will be stored for up to 1 year after the end of the study and destroyed after 1 year if not analyzed.

11.1.2.4. Potential Clinical Outcome Events

The events listed in [Section 12.1.6](#) will be initially assessed by the Investigator to determine if they are Potential Clinical Outcome Events. These events will be evaluated by an Adjudication Committee (described in [Section 13.4](#)) to confirm if they meet the criteria to be considered Clinical Outcome Events.

Given that the Potential Clinical Outcome Events could also meet the criteria of a suspected unexpected serious adverse reaction (SUSAR), which would necessitate unblinding for expedited reporting, the Sponsor will not expeditiously report suspected Potential Clinical Outcome events in order to retain the study blind and preserve the integrity of the clinical outcomes endpoint. These events will be selected as a “potential study event” on the Adverse Event eCRF and will be submitted for adjudication to the Adjudication Committee as described in [Section 13.4](#).

12. ASSESSMENT OF SAFETY

12.1. Adverse Events and Serious Adverse Events

12.1.1. Definitions of Adverse Events

12.1.1.1. Adverse Event

An AE is defined as any untoward medical occurrence associated with the use of the investigational product in humans, whether or not considered related to investigational product. An AE (also referred to as an adverse experience) can be any unfavorable and unintended sign (eg, an abnormal laboratory finding), symptom, or disease temporally associated with any use of the investigational product, without any judgment about causality and irrespective of route of administration, formulation, or dose, including an overdose.

AEs include, but are not limited to: (1) a worsening or change in nature, severity, or frequency of condition(s) present at the start of the study; (2) subject deterioration due to primary illness; (3) intercurrent illness; and (4) drug interaction. For reporting purposes, pregnancy is not considered an AE.

Subjects should be questioned in a general way, without leading the subject or asking about the occurrence of any specific symptom.

The Investigator should attempt to establish a diagnosis of the event based on signs, symptoms, and/or other clinical information. The diagnosis and not the individual signs/symptoms should be documented as the AE. For example, if the underlying disease process is a stroke, it would not be appropriate to record the AE by describing the symptoms “sudden numbness, dizziness, and difficulty speaking.” The AE medical term of “stroke or cerebrovascular accident” should be recorded as it more accurately describes the AE.

Subjects should be instructed to contact the site promptly upon awareness if they develop signs and symptoms of potential hepatic decompensation such as: pale-colored stools, urine color from pale to deep amber [dark], nausea, vomiting, abdominal pain, diarrhea, weight loss, fever and chills, fatigue, weakness, loss of appetite, confusion, swelling of the legs or abdomen, yellowing of the skin or whites of eyes, and bruising easily.

12.1.1.2. Serious Adverse Event

An AE is considered “serious” if, in the view of either the Investigator or Sponsor, it results in any of the following outcomes:

- Death
- Is immediately life threatening.
- Requires in-subject hospitalization or prolongation of existing hospitalization.
- Results in persistent or significant disability or incapacity.
- Results in a congenital abnormality or birth defect.
- Is an important medical event that may jeopardize the subject or may require medical intervention to prevent one of the outcomes listed above.

Events not considered to be SAEs are hospitalizations for:

- Routine monitoring of the studied indication and not associated with any deterioration in condition or AE.
- Elective treatment for a pre-existing condition that did not worsen.
- Respite care or observation when there is no AE associated with the hospitalization.

12.1.1.3. Treatment-Emergent Adverse Event

A treatment-emergent AE (TEAE) is any event not present prior to the initiation of the investigational product or any event already present that worsens in either intensity or frequency following exposure to the investigational product.

12.1.1.4. Adverse Events of Special Interest

The following decompensation events are adverse events of special interest. A subset of these events are also individual components of the primary endpoint ([Section 11.1.1](#)).

- Variceal bleeding or recurrent variceal bleeding documented by endoscopy OR patient presenting with anemia or melena (hemoglobin drop ≥ 2 gm/dL) and found to have varices documented by endoscopy, irrespective of hospitalization or requirement of blood transfusion.
- Gastrointestinal bleeding as a result of gastric or duodenal varices verified by endoscopy
- Hepatic encephalopathy, Grade ≥ 2
- New onset ascites requiring treatment
- Worsening of ascites (requiring increase in drug therapy or requirement of surgical procedure such as paracentesis or shunt placement)
- Refractory ascites -unresponsive to medications, and patient is not a candidate for TIPS or shunt and requires large volume paracentesis
- Hyponatremia ($\text{Na} \leq 125$ mEq/L) secondary to ascites
- Spontaneous bacterial peritonitis (confirmed by diagnostic paracentesis- by cell count/chemistry)
- Hepatorenal syndrome Type 1 and Type 2 and Acute Kidney Injury (AKI)
- Liver failure defined as worsening of liver synthetic function that is persistently worse relative to baseline and/or progressive over time.
 - Hepato-pulmonary syndrome
 - Porto-pulmonary syndrome
 - Liver Transplant
 - Increase in MELD scores by 3 points relative to baseline, persistent over time and unrelated to vitamin K deficiency related increase in INR
 - Any liver related event that requires hospitalization and treatment

12.1.1.5. Suspected Unexpected Serious Adverse Reaction

A suspected unexpected serious adverse reaction (SUSAR) is defined as a suspected adverse reaction which is assessed as serious, causally related to the investigational product, and unexpected per the reference safety information (RSI) in the Investigator's Brochure.

SUSARs are subject to expedited reporting. The Sponsor shall ensure that all relevant information about SUSARs that are fatal or life-threatening are recorded and reported as soon as possible to the relevant competent authorities (either directly or through the Eudravigilance Clinical Trials Module, as applicable), and to the Ethics Committees, no later than 7 days after knowledge by the Sponsor of such a case. Relevant follow-up information is subsequently communicated within an additional 8 days. All other SUSARs shall be reported to the competent authorities concerned (either directly or through the Eudravigilance Clinical Trials Module) and to the Ethics Committees concerned, within a maximum of 15 days of first knowledge by the sponsor. Each competent authority shall ensure that all SUSARs to an investigational product

which are brought to its attention are recorded. The Sponsor shall also inform all participating Investigators, as applicable to the local regulations.

12.1.2. Relationship to Investigational Product

The Investigator will document her/his opinion of the relationship of the AE to treatment with the investigational product using the criteria outlined in Table 9. An AE for which there is a ‘reasonable possibility’ that the investigational product caused the AE is otherwise referred to as suspected adverse reaction (SAR). “Reasonable possibility” means there is evidence to suggest a causal relationship between the investigational product and the AE.

If the relationship between the AE/serious adverse event (SAE) and the investigational product is determined to be “possible” or “probable” the event will be considered to be related to the investigational product for the purposes of expedited regulatory reporting.

Table 9: Relationship of Adverse Events to Investigational Product

Relationship	Description
Definite	A reaction that follows a reasonable temporal sequence from administration of the investigational product or in which the investigational product level has been established in body fluids or tissue; that follows a known or expected response pattern to the suspected investigational product; and that is confirmed by improvement on stopping or reducing the dosage of the investigational product, and reappearance of the reaction on repeated exposure.
Probable	A reaction that follows a reasonable temporal sequence from administration of the investigational product; that follows a known or expected response pattern to the suspected investigational product; that is confirmed by stopping or reducing the dosage of the investigational product; and that could not be reasonably explained by the known characteristics of the subject’s clinical state.
Possible	A reaction that follows a reasonable temporal sequence from administration of the investigational product; that follows a known or expected response pattern to the suspected investigational product; but that could readily be produced by a number of other factors.
Unlikely	A reaction that does not follow a reasonable temporal sequence from administration of the investigational product; that does not follow a known or suspected response pattern to the suspected investigational product; and that could reasonably be explained by known characteristics of the subject’s clinical state.
Not Related	Any event that does not meet the above criteria.

12.1.3. Relationship of Adverse Events to Liver Biopsy

The Investigator will document her/his opinion of the relationship of an AE to liver biopsy using the criteria outlined in [Table 10](#).

Table 10: Relationship of Adverse Events to Liver Biopsy

Relationship	Description
Related	A reaction that follows a reasonable temporal sequence from the liver biopsy; that follows a known or expected response pattern to the liver biopsy.
Not Related	Any event that does not meet the above criteria.

12.1.4. Recording Adverse Event Severity

AEs must be graded for severity (ie, intensity). A severity category of mild, moderate, or severe, as defined in Table 11, must be entered on the AE CRF. It should be noted that the term “severe” used to grade intensity is not synonymous with the term “serious.” The assessment of severity is made regardless of investigational product relationship or of the seriousness of the AE.

Table 11: Severity of Adverse Events

Grade	Clinical Description of Severity
1 = Mild	Causing no limitation of usual activities; the subject may experience slight discomfort.
2 = Moderate	Causing some limitation of usual activities; the subject may experience annoying discomfort.
3 = Severe	Causing inability to carry out usual activities; the subject may experience intolerable discomfort or pain.

12.1.5. Reporting of Adverse Events and Serious Adverse Events**12.1.5.1. Reporting of Adverse Events**

AE data will be collected from the time that signed informed consent is obtained until the subject fully completes her/his study participation.

All AEs, whether believed by the Investigator to be related or unrelated to the investigational product, must be documented in the subject’s medical records, in accordance with the Investigator’s normal clinical practice and on the AE eCRF. Each AE is to be evaluated for duration, intensity, frequency, seriousness, outcome, other actions taken, and relationship to the investigational product.

In addition, the Investigator should contact the study Medical Monitor upon awareness when any signs or symptoms of hepatic decompensation are observed in any subject.

12.1.5.2. Reporting of Serious Adverse Events

In agreeing to the provisions of this protocol, the Investigator accepts all legal responsibilities for immediate reporting of SAEs to the Sponsor. Immediate reporting implies within 24 hours of becoming aware of the occurrence of an SAE.

All SAEs must be reported to the Sponsor (including suspected liver-related clinical outcome events that qualify as serious).

SAEs are reported by entering the SAE data into the study-specific EDC system. Entering the SAE data into the EDC system will automatically notify the Sponsor of the event. In the event that the EDC system is inaccessible, an SAE may be reported by:

- E-mail to the SAE email address: [contact]
- Fax using a paper SAE report form: [contact]

If an SAE is reported by email or fax, an SAE Report form must also be completed in the EDC system as soon as the EDC system is accessible. At a minimum, the following information should be provided at the time of the initial report:

- Subject number
- Event term
- At least 1 criterion classifying the event as serious
- Name and title of the reporting individual
- Causal relationship to the investigational product

The Investigator will assess whether the event is causally related to the investigational product. The Sponsor will also assess whether the event is causally related to the investigational product, in addition to assessing the overall safety profile of the investigational product. The Sponsor will notify the appropriate regulatory agencies as well as all participating Investigators of Expedited Safety Reports that occur during the study within the time frames required by each regulatory agency.

Following the initial report, any additional information obtained by the Investigator about the SAE must be reported promptly to the Sponsor in the same manner as described above for the initial SAE report. Any supporting source documentation should be faxed to [contact] or emailed to [contact] as soon as possible. Redacted medical record source documentation will be requested for all SAEs and emergency room visits.

The Investigator is responsible for submitting information on Expedited Safety Reports received from the Sponsor to her/his local IRB/IEC, as directed by the local-country requirements. Documentation of the submissions to IECs/IRBs must be retained in the appropriate study file(s). As instructed by the Sponsor, Expedited Safety Reports should be retained in the appropriate investigative site study files or with the IB.

SAEs involving suspected liver-related clinical outcome events will be processed and reported by the Sponsor as described in Section 12.1.6.

12.1.6. Suspected Liver-Related Clinical Outcome Events

Specified liver-related clinical outcome events may, by definition qualify as SAEs (see [Section 12.1.1.2](#)). The Sponsor must be notified of any SAEs within 24 hours of the site becoming aware of the event (see [Section 12.1.5.2](#)). The Sponsor is responsible for regulatory reporting of SAEs, including expeditious reporting of SUSARs, which are defined as SAEs that are considered related (definitely, probably, or possibly related) to the investigational product and considered unexpected as defined in the IB.

Given that the liver-related clinical outcome events may also meet the criteria of a SUSAR, but are considered in aggregate as part of the primary endpoint and the DMC reviews of all safety and efficacy data approximately quarterly, the Sponsor will not expeditiously report suspected liver-related clinical outcome events in order to retain the study blind and preserve the integrity of the clinical outcomes endpoint. These events will be selected as a “study event” on the AE CRF and will be submitted for adjudication to the Hepatic Outcomes Committee as described in [Section 13.4](#).

The Sponsor will consider the following list of clinical outcome events (MedDRA preferred terms) to be disease related and exempt from expeditious regulatory reporting, but will continue to report them in a nonexpeditious manner: death, end-stage liver disease (preferred term: chronic hepatic failure), liver transplant (preferred term: liver transplant), HCC (preferred term: hepatocellular carcinoma), variceal bleeding (preferred term: gastroesophageal variceal haemorrhage or oesophageal varices haemorrhage), hepatic encephalopathy (preferred term: hepatic encephalopathy), spontaneous bacterial peritonitis (preferred term: peritonitis bacterial), ascites (preferred term: ascites), and histological or clinical progression to cirrhosis (preferred term: hepatic cirrhosis).

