5.7. Summary of Known Potential Risks with OCA

The rate of progression and risk of decompensation is variable and may be rapid in certain patients, necessitating closer surveillance of patients at risk.

Clinical Data

In two Phase 2 studies and a Phase 3 study evaluating OCA in the treatment of subjects with PBC, hepatic adverse events, including jaundice, worsening ascites and primary biliary cholangitis flare, were observed in subjects receiving doses of OCA ranging from the maximum approved dose of 10 mg once daily to 50 mg (5 times the highest recommended dose), as early as one month after starting treatment with OCA.

In addition, safety findings in NASH clinical trials include 2 cases of hepatic decompensation reported as SUSARs, 1 of which resulted in death. Both cases involved numerous confounding factors that make evaluation of association with treatment difficult. Details for both events are provided in the current version of the OCA Investigator's Brochure.

The primary AE shown to be related to OCA is pruritus. Pruritus has also been observed in clinical studies with OCA in other indications, as well as in healthy subjects, with the highest frequency observed in subjects with PBC. The incidence and severity of pruritus have been shown to be dose dependent, but there is no evidence of association with stage or progression of underlying disease.

Changes in lipid profiles have also been observed with OCA dosing, including an increase in low density lipoprotein (LDL) cholesterol and a decrease in high-density lipoprotein (HDL) cholesterol. The clinical significance of these lipid findings remains unclear and is being studied further.

An independent data monitoring committee (DMC) has performed detailed reviews of individual subject and aggregate data from both the Phase 3 clinical outcomes study in subjects with PBC (Study 747-302) and the Phase 3 pivotal studies in subjects with NASH fibrosis (Study 747-303) and NASH cirrhosis (Study 747-304) on a quarterly basis, in an unblinded fashion, and in closed sessions (without the Sponsor's participation). In the quarterly DMC meetings to date, the DMC has recommended the studies continue without modification.

Following a request from the FDA to provide an up-to-date DMC report analyzing unblinded data on respective incidence of cholecystitis, cholelithiasis, and pancreatitis by treatment group across all ongoing clinical studies, an ad hoc DMC review was held and the DMC recommended that:

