6. STUDY OBJECTIVES AND PURPOSE

6.1. Primary Objective

To assess the effect of OCA compared to placebo, in conjunction with established local standard of care on clinical outcomes in subjects with PBC as measured by time to first occurrence of any of the following adjudicated events, derived as a composite event endpoint:

- Death (all-cause)
- Liver transplant
- Model of end stage liver disease (MELD) score ≥ 15
- Hospitalization (as defined by a stay of 24 hours or greater) for new onset or recurrence of:
 - Variceal bleed
 - Hepatic encephalopathy (as defined by a West Haven score of ≥ 2)
 - Spontaneous bacterial peritonitis (confirmed by diagnostic paracentesis)
- Uncontrolled ascites (diuretic resistant ascites requiring therapeutic paracentesis at a frequency of at least twice in a month)

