13.3. Data Monitoring Committee

An independent DMC that includes hepatologists, pharmaceutical physicians, epidemiology/cardiology expert(s), and statistician(s) not involved in the study as Investigators, adjudication committee members, or consultants. The DMC will have oversight over the study

conduct as defined by the DMC charter. All members will have considerable experience with clinical study conduct and DMCs. Any candidate found to have a conflict of interest or whose name is listed on the FDA debarment list will not be offered membership. Conflicts of interest will be assessed regularly, and if members are found to have a new conflict of interest they will be replaced.

The DMC will meet approximately quarterly at scheduled meetings and ad hoc meetings will be convened, as appropriate, to review safety and efficacy data in order to ensure the safe and proper treatment of subjects. Based on review of these data, the DMC will advise the Sponsor on the validity and scientific merit of continuing the study.

Written minutes of both the open and closed DMC sessions will be prepared. The closed minutes will be made available to the appointed Sponsor representatives only after the database is locked.

Data listings provided to the DMC do not contain individual subject treatment information; however, the DMC will have access to the database and may unblind individual subject data as appropriate. Summary tables reviewed by the DMC during closed sessions will include an overall column containing information regarding all subjects and separate treatment columns with 'dummy' labels, ie, the actual treatment groups are used, but are not identified. Data reviewed during the meetings will include, at a minimum, disposition, demographics, exposure, clinical laboratory results, Medical Dictionary for Regulatory Activities (MedDRA) coded AEs, and AEs leading to early withdrawal of investigational product. At each meeting, detailed narratives of interval SAEs (including events resulting in death) are reviewed by the DMC in addition to a cumulative list of all SAEs.

The DMC may agree to adjust meeting frequency based upon actual and projected safety and efficacy data availability. Adjustments to or stopping of the protocol defined doses may be considered based on DMC evaluation of OCA safety and tolerability.

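### The reason given in Section 12.1.6 for not expediting outcome events covers primary-endpoint events only, but the exempt list is wider than the composite, and its unqualified 'death' conflicts with the 7-day rule for fatal SUSARs

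*Protocol*

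**What the plan says.** Section 12.1.6 accepts that liver-related outcome events may meet SUSAR criteria. It explains that they will not be expedited because they may be SUSARs "but are considered in aggregate as part of the primary endpoint and the DMC reviews of all safety and efficacy data approximately quarterly", and because the blind and the outcome endpoint must be protected. It then names the terms that the sponsor will consider "to be disease related and exempt from expeditious regulatory reporting, but will continue to report them in a nonexpeditious manner: death, end-stage liver disease". The list goes on to include "HCC (preferred term: hepatocellular carcinoma", and it ends with "ascites (preferred term: ascites), and histological or clinical progression to cirrhosis (preferred term: hepatic cirrhosis".

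The primary composite is set out in Sections 6.1, 11.1.1 and 13.1.3. It includes "Death (all-cause"), so deaths of every cause count. It does not include HCC or progression to cirrhosis, which Sections 6.2, 11.1.2 and 13.1.5 treat as secondary.

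Section 12.1.1.5 gives the general rule. All relevant information about "SUSARs that are fatal or life-threatening are recorded and reported as soon as possible to the relevant competent authorities" within 7 days, and other SUSARs are due within 15 days. It mentions no exemption. Section 12.1.5.2 sends serious events involving suspected liver-related outcomes to Section 12.1.6, and Section 11.1.2.4 repeats the decision not to expedite.

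**The concern.** Exempting endpoint events from expedited reporting is a recognisable way to protect the blind in an outcome trial, but the exemption can reach only as far as its reason. Here the only endpoint cited is the primary one, and several listed terms are not primary events or are so only under conditions that the list omits. Followed as written, a suspected, unexpected, serious reaction coded to one of those terms would reach authorities by the slower route on a justification that does not apply to it.

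The terms are not remote from the drug's suspected risks. Section 5.7 says that in the earlier PBC studies "hepatic adverse events, including jaundice, worsening ascites and primary biliary cholangitis flare, were observed in subjects receiving doses of OCA", as early as one month after the start of treatment. It also says that two cases of hepatic decompensation in NASH trials of OCA, one of them fatal, were reported as SUSARs. Events of this kind have therefore been handled as SUSARs elsewhere in the programme.

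Death raises a separate problem. The list labels every death disease related, whereas Section 12.1.1.5 puts a fatal suspected unexpected reaction on a 7-day clock.

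**Working it through.** The plan states no figure to reproduce. The check compares the list in Section 12.1.6, term by term, with the composite in Section 11.1.1.

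| Exempt term (12.1.6) | Condition in the primary composite (11.1.1) | Covered by the stated reason? |
|---|---|---|
| Death | All causes | Yes |
| Liver transplant | None | Yes |
| End-stage liver disease | Not named; nearest item is MELD of 15 or more | Not counted either way |
| Variceal bleeding | Hospital stay of at least 24 hours | Partly |
| Hepatic encephalopathy | Same hospital condition, and West Haven 2 or higher | Partly |
| Spontaneous bacterial peritonitis | Same hospital condition, confirmed by diagnostic paracentesis | Partly |
| Ascites | Diuretic-resistant, with therapeutic paracentesis at least twice in a month | Partly |
| HCC | Absent (secondary) | No |
| Progression to cirrhosis | Absent (secondary) | No |

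Count: 2 covered + 1 uncounted + 4 partly covered + 2 not covered = 9.

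Other parts of the protocol support this reading. Section 12.1.1.4 says that only some of the decompensation events of special interest are primary components, and it lists new-onset and worsening ascites separately. Appendix I records that HCC was moved from the primary composite to the secondary endpoints in Version 4. That may explain why it is still on the exempt list.

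**Deaths.** Section 12.1.1.5 sets 7 days for a fatal SUSAR. Section 12.1.6 sets no expedited deadline for death, with no restriction on cause. The heading of Section 12.1.6, its operative sentence and the routing sentence in Section 12.1.5.2 all concern liver-related events. A fatal non-hepatic reaction that is suspected and unexpected is thus inside the list by its wording and outside the section by its subject. The protocol clearly expects non-hepatic deaths: it separates liver-related from all-cause death (Sections 13.1.5 and 13.1.8) and sends all deaths to the cardiovascular committee as well as the hepatic one (Section 13.4).

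**Adjudication.** The exemption attaches to suspected events, and Section 11.1.2.4 leaves confirmation to the committee. Neither section says whether a related, unexpected event that the committee rejects returns to the route in Section 12.1.1.5.

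**The case against.** The strongest reply is that this is a general rule with a signposted exception. Section 12.1.5.2 points to Section 12.1.6 and Section 11.1.2.4 repeats the exception, so for liver-related events the lack of a pointer in Section 12.1.1.5 is a drafting gap. That stands for liver-related events. It does not settle non-hepatic deaths, which the routing sentence does not mention.

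A second reply is that HCC and cirrhosis are outcome endpoints too, and that unblinding a subject at first ascites would reveal treatment before any later primary event. This has force: a separate reason for those terms could be given, and it would be wrong to say that blinding has no bearing on them. But Section 12.1.6 gives no such reason, and Section 9.4.1 already gives designated safety staff access to treatment assignments for SUSAR reporting.

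A third is practical. Status as a primary event is confirmed only by later adjudication, and uncontrolled ascites needs two paracenteses within a month, while the reporting clocks run 7 or 15 days. That is right, so any alignment has to be with suspected primary events.

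A reader might also infer that the DMC would not see these events, because Section 13.3 begins "Data reviewed during the meetings will include, at a minimum, disposition, demographics, exposure, clinical laboratory results" and does not name outcome events. The text does not support that. The same sentence goes on to coded adverse events, and the section provides narratives of new serious events including deaths, a cumulative list, tables by arm under masked labels, and the power to unblind a subject. Serious events also reach the sponsor within 24 hours.

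**Conclusion.** The concern holds as a mismatch between a stated reason and its list, plus an unresolved conflict over deaths. Two of nine exempt categories lie wholly outside the primary composite and four lie partly outside it. For a fatal suspected unexpected reaction, the two sections give either 7 days or no expedited deadline. The number of reports affected cannot be derived from the protocol. The primary analysis is not touched.

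Two stronger readings should be resisted. One is that death shows the list exceeding its reason. It does not, because all-cause death is a primary component; only the disease-related label and the conflict with Section 12.1.1.5 are at fault. The other is that known OCA harms escape expediting. A SUSAR must be unexpected against the reference safety information in the Investigator's Brochure, which is not shown, so a harm already listed there would not be expedited under any wording. The point is limited to events assessed as serious, related and unexpected.

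**What to change.** Reconcile Section 12.1.6 with Sections 11.1.1 and 12.1.1.5.

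- Align the exempt list with the suspected primary-endpoint events that the stated reason covers. HCC, progression to cirrhosis and ascites not suspected to be uncontrolled should not be exempt on that reason. Reconcile the bleeding, encephalopathy and peritonitis terms with their conditions in the composite.
- Cross-reference the exemption in Section 12.1.1.5, so that the general rule and the exception can be read together.
- Reconcile the unqualified entry for death with the 7-day rule, stating how non-hepatic deaths assessed as related and unexpected are reported.
- State how events rejected at adjudication are reported.

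No change to the DMC listings is needed, and death need not be narrowed to disease progression, since all-cause death is a primary component. The cost is protocol wording and a few more single-subject unblindings by the designated safety staff already provided for in Section 9.4.1.
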